6.5. Concomitant Therapy

The use of any concomitant medication, prescription or over-the-counter, is to be recorded on the subject's electronic case report form (eCRF) at each visit, along with the reason the medication is taken, the dates of administration, and the dose.

6.5.1. Prohibited Drugs and Washout Before the Study

Table 6-1 provides a list of specific restrictions for concomitant therapy use during the study, with any necessary washout periods described (see [Section 6.5.2](#) for permitted medications requiring a stable dose prior to study entry and **Table 6-1** for the list of prohibited medications and washout periods). For subjects who had a positive urine drug screen at Visit 1 due to a prohibited concomitant medication, the urine drug screen must be repeated at Visit 2 to determine if sufficient washout of the prohibited concomitant medication has occurred and to confirm eligibility. The urine drug screen does not need to be re-tested at Visit 2 if the initial positive result at Visit 1 was due to a permitted concomitant medication based on the clinical judgment of the Investigator.

If there is a clinical indication for any therapy that is specifically prohibited during the study, discontinuation from study drug may be required. The Investigator should discuss any questions regarding this with the Sponsor's designated Medical Monitor. The final decision on any supportive therapy rests with the Investigator and/or the subject's primary physician. However, the decision to continue the subject on study treatment requires the mutual agreement of the Investigator and the Sponsor's designated Medical Monitor.

Consult the Sponsor's designated Medical Monitor if there is any uncertainty regarding subject use of a particular drug or drug class.

Table 6-1 Prohibited Medications

Class	Examples	Washout Period
Mu-opioid receptor agonist	eluxadoline	1 month prior to Run-in (Visit 2)
Opiates and narcotic pain-relievers	morphine, codeine, paregoric, opium, propoxyphene, fentanyl, methadone	14 days prior to Run-in (Visit 2)
Beta agonists	mirabegron, dobutamine, isoprenaline, albuterol (systemic only)	14 days prior to Run-in (Visit 2)
Musculoskeletal drugs	baclofen, cyclobenzaprine, methocarbamol, metaxalone	14 days prior to Run-in (Visit 2)
Previous use of antibiotics to treat IBS	rifaximin, neomycin	90 days prior to Run-in (Visit 2)
Antibiotics ^a	amoxicillin, doxycycline, cephalexin, ciprofloxacin	14 days prior to Run-in (Visit 2)
Psychoactive drugs used to treat IBS	cannabis products (including systemic cannabidiol [CBD])	14 days prior to Run-in (Visit 2)
CNS stimulants	cocaine, amphetamines	14 days prior to Run-in (Visit 2)
Barbiturates	Phenobarbital ^b , secobarbital	14 days prior to Run-in (Visit 2)
NMDA receptor agonist	phencyclidine	14 days prior to Run-in (Visit 2)

CNS = central nervous system; IBS = irritable bowel syndrome; NMDA = N-methyl-D-aspartate

^a Antibiotics are permitted during the Treatment Period as needed.

^b Unless prescribed and at stable doses as anticonvulsant for documented epilepsy.

6.5.2. Permitted Drugs

Medications listed in [Table 6-2](#) are permitted as long as the dose has been stable for the specified time period.

Table 6-2 Medications Permitted at Stable Doses

Class	Examples	Stable Dose Period
Anticonvulsants for subjects with documented epilepsy	Carbamazepine, gabapentin, pregabalin, topiramate	6 months prior to Run-in (Visit 2)
Antidepressants	Tricyclic antidepressants, trazodone, SNRIs (eg, duloxetine), SSRIs	3 months prior to Run-in (Visit 2)
Antihypertensives	Diuretics, ACE inhibitors, calcium channel blockers, angiotensin receptor blockers, beta blockers, alpha agonists	3 months prior to Run-in (Visit 2)
Injectable and standard therapy for acute, episodic or chronic migraine unless prohibited (Section 6.5.1)	Botulinum toxin A injections, erenumab or other CGRP antagonists if approved, triptans	1 month prior to Run-in (Visit 2)
Antispasmodics/smooth muscle relaxants and peppermint oil	Otilonium, pinaverium, hyoscyamine, dicyclomine, peppermint oil, butylscopolamine	1 month prior to Run-in (Visit 2)

ACE = angiotensin-converting enzyme; CGRP = calcitonin gene-related peptide; SNRI = serotonin-norepinephrine reuptake inhibitor; SSRI= Selective Serotonin reuptake inhibitor

Medications for the treatment of allergies, chronic medical conditions, and acute migraines are permitted with the exception of prohibited pain medications (see [Section 6.5.1](#)). As needed, the use of benzodiazepines for anxiety is permitted.

With the exception of the agents specified in [Table 6-1](#) and the medications requiring stable doses prior to study entry ([Table 6-2](#)), any other concomitant medication deemed necessary for the welfare of the subject during the study may be given at the discretion of the Investigator. If the permissibility of a specific medication/drug is in question, please contact the Sponsor's designated Medical Monitor. Any medication or vaccine (including over-the-counter or prescription medicines, vitamins, and/or herbal supplements) that the subject is receiving at the time of enrollment or receives during the study must be recorded in the eCRF. Allowed rescue medication for pain, constipation, and diarrhea are listed in [Section 6.5.3](#).

6.5.3. Rescue Medicine

Rescue medications should only be used starting at Day 1 (Visit 3) or after. The following rescue medications may be used:

For pain

- Equivalent of ibuprofen 400 mg twice daily or less
- Low-dose acetaminophen 500 mg three times daily or less
- Low-dose aspirin (\leq 325 mg daily)

For constipation (not thought to affect IBS pain)

- Polyethylene glycol
- Bisacodyl (no more than one 5-mg dose weekly)

For diarrhea (not thought to affect IBS pain)

- Loperamide (up to 4 mg four times daily)

Rescue medications will not be provided by the Sponsor.

Use of rescue medication will be collected on the daily diary (ie, subjects will respond to prompts asking if any rescue medication was taken for abdominal pain or stool symptoms). During the subsequent subject visit, the details of the rescue medication will be collected for inclusion on the concomitant medication eCRF page, as needed.

6.6. Dose Modification

No dose modification of study drug is permitted. Study drug should be withheld for liver test abnormalities as described in [Section 8.4.7.1](#).

6.7. Drug after the End of the Study

No further study drug will be administered to subjects who complete the study.

7. Discontinuation of Study Drug and Subject Discontinuation/Withdrawal

A premature discontinuation will occur if a subject who signs the informed consent form (ICF) and is randomized ceases participation in the study, regardless of circumstances, before the completion of the protocol-defined study procedures.

7.1. Discontinuation of Study Drug

Subjects who discontinue study drug post-randomization will complete the Week 12/Early Withdrawal assessments specified in the Schedule of Assessments ([Section 1.3](#)). Reasons for discontinuation from double-blind study drug treatment and the study include the following:

- Adverse event (AE)
- Lack of efficacy
- Noncompliance
- Withdrawal of consent
- Lost to follow-up
- Physician decision
- Protocol deviation
- Pregnancy
- Death
- Other

Discontinuation of study drug for abnormal liver function should be considered by the Investigator when a subject meets all of the conditions outlined in [Section 8.4.7.2](#) for Hy's law or if the Investigator believes that it is in the best interest of the subject (reason for discontinuation will be AE). Reporting and follow-up requirements for pregnancy are provided in [Section 8.4.5](#) and [Section 10.6.2](#).

For subjects who are not randomized into the 12-week double-blind treatment period and, therefore, are either screen failures or run-in failures, the End of Study eCRF should be completed (refer to eCRF completion guidelines for additional information).

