If **any** of the following liver test abnormalities develop, study drug should be withheld immediately with appropriate clinical follow-up (including repeat laboratory tests, until a subject's laboratory profile has returned to normal/baseline status), and the event reported as an SAE:

- ALT or AST $> 8 \times$ upper limit of normal (ULN)
- ALT or AST $> 5 \times$ ULN and persists for more than 2 weeks
- ALT or AST $> 3 \times$ ULN and total bilirubin $> 2 \times$ ULN or international normalized ratio (INR) > 1.5
- ALT or AST $> 3 \times$ ULN with appearance of fatigue, nausea, vomiting, right upper quadrant pain or tenderness, fever, rash and/or eosinophilia ($> 5\%$)

Rechallenge may be considered if an alternative cause for the abnormal liver tests (ALT, AST, total bilirubin) is discovered and the laboratory abnormalities resolve to normal or baseline values. The Investigator and Sponsor's designated Medical Monitor must discuss and agree with any decision to rechallenge.

Rechallenge should not occur when the etiology of the liver test abnormalities is considered possibly drug-induced.

8.4.7.2. Criteria for Permanent Discontinuation of Study Drug in Association with Liver Test Abnormalities

Study drug should be discontinued permanently if **all** of the following 4 criteria are met (ie, potential severe drug-induced liver injury/Hy's law case):

- Total bilirubin increases to $> 2 \times$ ULN or INR > 1.5 **and**
- AST or ALT increases to $\geq 3 \times$ ULN **and**
- Alkaline phosphatase value does not reach $2 \times$ ULN **and**
- No alternative cause explains the combination of the above laboratory abnormalities; important alternative causes include, but are not limited to, the following:
 - Hepatobiliary tract disease
 - Viral hepatitis (eg, hepatitis A/B/C/D/E, Epstein-Barr virus)
 - Exposure to hepatotoxic agents/drugs or hepatotoxins, including herbal and dietary supplements, plants, and mushrooms;
 - Alcoholic hepatitis
 - Non-alcoholic steatohepatitis

- Autoimmune hepatitis

If an alternative cause for hepatotoxicity is identified, then it should be determined (based on the severity of the hepatotoxicity or event) whether study drug should be withheld or permanently discontinued as appropriate for the safety of the subject, following consultation with the Sponsor's designated Medical Monitor.

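### Protocol 7.1 asks the Investigator only to consider stopping study drug in a Hy's law case, whereas 8.4.7.2, which it cites, directs permanent stopping (minor inconsistency)

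*Protocol*

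**What the plan says.** **Protocol 7.1 (Discontinuation of Study Drug).** "Discontinuation of study drug for abnormal liver function should be considered by the Investigator when a subject meets all of the conditions outlined in". The conditions meant are the Hy's law criteria in 8.4.7.2. The same sentence adds a second ground, the Investigator's view of the subject's best interest, and gives AE as the reason to be recorded. One verb phrase governs both grounds.

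**Protocol 8.4.7.2.** The heading is "Criteria for Permanent Discontinuation of Study Drug in Association with Liver Test Abnormalities". The operative sentence begins "Study drug should be discontinued permanently if" and requires all four criteria:

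1. total bilirubin above 2 x ULN or INR above 1.5;
2. "AST or ALT increases to" 3 x ULN or more;
3. alkaline phosphatase not reaching 2 x ULN;
4. "No alternative cause explains the combination of the above laboratory abnormalities".

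A choice between withholding and stopping is left open only where another cause has been identified.

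**Protocol 8.4.7.1.** If any of four triggers occurs, "study drug should be withheld immediately with appropriate clinical follow-up", "and the event reported as an SAE". One trigger is ALT or AST above 3 x ULN together with bilirubin above 2 x ULN or INR above 1.5. Rechallenge needs an alternative cause, resolved laboratory values, and agreement between the Investigator and the Medical Monitor. The section adds: "Rechallenge should not occur when the etiology of the liver test abnormalities is considered possibly drug-induced".

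**Consequences of formal discontinuation.** Under 7.1 the woman completes the Week 12/Early Withdrawal assessments. Under 7.2 she also leaves the study. SAP 7.3 tabulates TEAEs that lead to discontinuation of study treatment.

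**The concern.** A stopping rule for potential severe drug-induced liver injury should give the same instruction wherever it appears. Section 7.1 carries the title under which a site would look for the rule, and it gives the weaker version. The documents do not say which section prevails. One site could follow 7.1, keep the woman on hold and leave her status open, while another stops drug and withdraws her for the same findings. At stake is uniform handling of a rare but important case: the recorded reason, the Early Withdrawal visit, withdrawal under 7.2, and the count in one safety table. Sample size, power and the efficacy estimates are not involved.

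**Working it through.** The main point needs no arithmetic, because it compares two current texts. A short criteria check then shows how far 8.4.7.1 limits the consequence.

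**Step 1. Same trigger.** The Hy's law clause of 7.1 sets no liver limits of its own. It applies when all conditions of 8.4.7.2 are met, so both sections address the same women.

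**Step 2. Different action.** In 7.1 the Investigator is to consider discontinuation. In 8.4.7.2 drug is to be stopped for good. Both use *should*, but the action attached to it differs.

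**Step 3. Can they be reconciled?** The only discretion in 8.4.7.2 depends on an alternative cause being identified. Criterion 4 requires that there is none. That discretion cannot cover the women described in 7.1.

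**Step 4. Does 8.4.7.1 already take them off drug?** Its bilirubin/INR trigger uses the same bilirubin and INR limits as criterion 1 of 8.4.7.2. So any 8.4.7.2 case with ALT or AST above 3 x ULN also meets that trigger. The exception is a highest value of exactly 3.0 x ULN, because 8.4.7.2 uses >= 3 and the lowest ALT/AST limit in 8.4.7.1 is > 3.

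Illustration with assumed values: total bilirubin 2.5 x ULN, INR 1.0, alkaline phosphatase 1.0 x ULN, no alternative cause, no listed symptoms or eosinophilia, no elevation above 5 x ULN lasting more than 2 weeks, AST no higher than ALT.

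| ALT (x ULN) | Criteria met, 8.4.7.2 | Triggers met, 8.4.7.1 | In SAP 7.4 Hy's law display |
|---|---|---|---|
| 2.9 | 3 of 4 | 0 of 4 | no |
| 3.0 | 4 of 4 | 0 of 4 | yes |
| 3.1 | 4 of 4 | 1 of 4 | yes |
| 4 | 4 of 4 | 1 of 4 | yes |
| 6 | 4 of 4 | 1 of 4 | yes |
| 9 | 4 of 4 | 2 of 4 | yes |

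With >= 3 in the bilirubin/INR trigger, the 3.0 row becomes 4 of 4 and 1 of 4.

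**Step 5. Where would the case be reported if drug were only withheld?**

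- The table of TEAEs leading to discontinuation (SAP 14.3.2.11) would not include her.
- The listing of TEAEs leading to withdrawal or interruption (SAP 14.3.2.20) would.
- The AESI summaries would, because the liver AESI covers both temporary withholding and permanent stopping.
- The potential Hy's law display in SAP 7.4 (ALT or AST >= 3 x ULN with bilirubin >= 2 x ULN) would, provided she qualifies through bilirubin. A case qualifying on INR alone would not enter that display, but this is so whichever section the site follows.

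**The case against.** The strongest reply is that 7.1 sends the reader to 8.4.7.2, whose heading and first sentence are unambiguous, so a site that follows the reference gets the firm instruction. Drug is also already withheld under 8.4.7.1 above 3 x ULN. Rechallenge requires an alternative cause, and a woman who meets criterion 4 has none. While she meets the criteria there is no compliant route back to study drug. Sections 8 and 8.3 also call for immediate discussion of safety concerns with the Medical Monitor.

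Most of this stands, and it rules out two stronger readings that a reader might infer:

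- **That the protocol lets a Hy's law case stay on drug.** The documents do not support this. Above 3 x ULN, 8.4.7.1 takes her off drug. At exactly 3.0 x ULN, 8.4.7.2 still directs stopping.
- **That a withheld case would disappear from the safety report.** It would not. The outputs in Step 5 still capture her, and SAE follow-up under 8.4.3 does not depend on discontinuation.

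A reader might also see a gap in Protocol 6.6, which cites only 8.4.7.1. That section concerns dose modification, where withholding is the relevant action. Permanent stopping belongs in Section 7, which does cite 8.4.7.2, so 6.6 needs no change.

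The reply does not remove the conflict itself. The section that governs discontinuation gives a weaker instruction than the section it relies on, for the same women.

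**Conclusion.** The point holds as a minor inconsistency in a safety stopping rule. It is an error in current operative text, not an effect of redaction or of superseded wording. The practical effect is confined to formal discontinuation and withdrawal status, the procedures that follow from it, and one TEAE table.

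Few or no cases are expected: exclusion criterion 33 removes women with ALT or AST above 2.0 x ULN at entry, and 8.4.7 reports no liver-toxicity concern to date. The > 3 versus >= 3 difference is a separate and smaller matter that bears only on a value of exactly 3.0 x ULN. What is missed there is the instruction to withhold at once and report as an SAE.

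The wording conflict needs no numerical assumption. The criteria check rests on the assumed case above and on reading the 8.4.7.1 trigger as ALT or AST above 3 x ULN combined with either the bilirubin or the INR condition.

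**What to change.** Reword the liver sentence in 7.1 to match 8.4.7.2, for example: *Study drug should be discontinued permanently when all conditions in Section 8.4.7.2 are met. Discontinuation may also be considered where the Investigator judges it to be in the subject's best interest. In either case the recorded reason is AE.* If *must* is preferred, use it in both 7.1 and 8.4.7.2.

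Optionally, change the ALT/AST limit in the bilirubin/INR trigger of 8.4.7.1 from > 3 to >= 3 x ULN. Every 8.4.7.2 case then also falls under the instruction to withhold at once and report as an SAE, and the limit matches the one in SAP 7.4.

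The cost is one sentence and, if the option is taken, one inequality sign, in the next amendment. The SAP, data collection and sample size do not change.

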7.2. Subject Discontinuation/Withdrawal from the Study

- Subjects who discontinue post-randomization study drug will also withdraw from the study.
- A subject may choose to withdraw from the study at any time at her own request, or may be withdrawn at any time at the discretion of the Investigator for safety, behavioral, compliance, or administrative reasons.
- If a subject withdraws consent for disclosure of future information, the Sponsor or designee may retain and continue to use any data collected before such a withdrawal of consent.
- If a subject withdraws from the study, she may request destruction of any blood or urine samples taken and not tested, and the Investigator must document this in the site study records.
- Subjects who withdraw from the study will not be replaced (enrollment accounts for a predetermined dropout rate).
- The Week 12/Early Withdrawal assessments will be completed, if possible, when a subject withdraws or is withdrawn from the study (see Schedule of Assessments in [Section 1.3](#)).

7.3. Lost to Follow-up

Should a subject fail to attend a required study visit, the site should attempt to contact the subject and reschedule the missed visit as soon as possible. The site should also counsel the subject on the importance of maintaining the assigned visit schedule and ascertain whether or not the subject wishes to and/or should continue in the study based on previous noncompliance. In cases where the subject does not return for the rescheduled visit or cannot be reached to reschedule the missed visit, the site should make every effort to regain contact with the subject so that they can appropriately be withdrawn from the study with a primary reason of “Lost to Follow-up”, including at least three documented attempts to contact the subject (ie, phone, email, or certified letter). Efforts to establish the possible reason for discontinuation should be documented.

7.4. Early Study Termination

The Sponsor reserves the right to terminate the study at any time. The study may be terminated early if the extent (incidence and/or severity) of emerging effects/clinical endpoints is such that the risk/benefit ratio to the study population as a whole is unacceptable. In addition, further recruitment in the study overall or at a particular study site may be stopped due to insufficient compliance with the protocol, Good Clinical Practice or other applicable regulatory requirements; procedure-related problems; or the number of discontinuations for administrative reasons is too high.

8. Study Assessments and Procedures

Study procedures and their timing are summarized in the Schedule of Assessments ([Section 1.3](#)). A detailed listing of study assessments by visit is provided in [Section 10.7](#).

- Protocol waivers or exemptions are not allowed; however, subjects who fail to meet eligibility criteria may be rescreened once, as appropriate. Any notable protocol deviations should be noted and raised to the Sponsor's or designee's attention.
- Immediate safety concerns should be discussed with the Sponsor's designated Medical Monitor immediately upon occurrence or awareness to determine if the participant should continue or discontinue study drug.
- Adherence to the study design requirements, including those specified in the Schedule of Assessments, is essential and required for study conduct.
- Note that patient-reported outcome (PRO) assessments will be completed prior to vital signs, and vital signs will be taken prior to blood draws.

8.1. Baseline Procedures

8.1.1. Informed Consent

Documented consent must be obtained from each potential subject prior to participating in any study procedures according to the process described in [Section 10.1.3](#).

8.1.2. Assignment of Subject Number

All subjects who sign the ICF will be assigned a unique subject number by IWRS. This number will be used to identify the subject throughout the study. Subjects who are rescreened will be assigned a new subject number. If a new number is assigned, the subject will be linked to both subject numbers.

8.1.3. Screening

All screening evaluations must be completed and reviewed to confirm that potential subjects meet all eligibility criteria. The Investigator will maintain a screening log to record details of all subjects screened and to confirm eligibility or record reasons for screening failure, as applicable. Inclusion and exclusion criteria ([Section 5.1](#) and [Section 5.2](#)) will be reviewed by the Investigator or qualified designee at Screening, the start of the Run-in Period, and the start of the double-blind Treatment Period.

Subjects who fail to meet entry criteria may be rescreened **once** upon consultation with, and approval by, the Sponsor's designated Medical Monitor, Sponsor, or designee (See [Section 8.1.2](#) regarding subject number).

The Screening Period may also be used for washout of prohibited medications (see [Section 6.5.1](#)).

8.1.4. Medical History

A medical history will be obtained by the Investigator or qualified designee. Medical history will include all chronic and ongoing conditions, regardless of year diagnosed; surgical history; substance abuse history; and IBS history (eg, Rome subtype, date of diagnosis, prior treatment). A history of previous diets for IBS and their perceived effectiveness will also be collected. All events occurring after the subject signs the ICF will be recorded as AEs.

8.1.5. Demographics

Demographic data collection will include sex, age, race, and ethnicity.

